Surgical excisional debridement is the main stay of management with necessary decompression, lavage, debridement, and partial synovectomy. However, there has been considerable debate over the optimal modality. Most surgeons perform an open arthrotomy or arthroscopic debridement, although serial aspiration can be considered as an option in very limited circumstances with patients who cannot tolerate surgery. While open arthrotomy has been often utilized, there has been an increasing number of proponents for arthroscopic treatment citing lower re-infection rates and better functional outcomes. However, there has been a lack of well-designed prospective studies comparing surgical treatment modalities for native knee septic arthritis. The goals of this present study are to determine if arthroscopic management of septic arthritis in the native knee resulted in lower number of surgeries and shorter length of stay compared to open arthrotomy. Secondary outcomes included differences in functional outcome and overall patient satisfaction.

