**Background (literature review):** Please see abstract

**Specific Aims:** To determine if there is an overall difference in hospital length of stay and number of surgeries required to provide clinical resolution of septic arthritis of an adult native knee. Secondary outcomes will evaluate differences in knee range of motion, post operative pain levels, and overall patient satisfaction.

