If the diagnosis of septic arthritis has been established, the diagnosis, pathogenesis and treatment options will be discussed with the patient. The current standard of care for the management of septic arthritis in the knee is operative incision and drainage of the joint with debridement and irrigation, obtaining intra operative cultures, then initiating antibiotic therapy. Non operative management would consist of antibiotic treatment alone. Should the patient decide to proceed with surgical intervention, an informed consent for surgery in the presence of a witness will be obtained, as per standard guidelines. At that time, the patient will be asked to participate in this study. If they agree, then the patient will be randomized into one of two groups:

1. Open surgical incision and drainage with debridement and irrigation
2. Arthroscopic incision and drainage with debridement and irrigation

An informed consent will be performed by one of the participating research investigators in the setting of a witness, as per standard guidelines. The surgical consent will be obtained at that time in a similar manner. If the patient declines to participate in this study, they will still be offered surgical intervention based on physician preference and their surgical ability.

All patients will be admitted after surgery for continued intravenous antibiotics and infectious disease consultation. Additionally, they will be followed for signs/symptoms that indicated a second surgery is required. The specific criteria for recurrence and failure of initial irrigation and debridement will be the following:

- persistent purulent discharge from a drain or incisional site
- increasing pain
- decreasing range of motion
- persistent fevers
- persistent elevation of serologic inflammatory markers

Patients showing steady clinical improvement after 72 hours post operatively will be discharged with continued antibiotic therapy targeted to bacteria if positive growth on cultures. If delayed growth occurs after patient discharge, they will be individually contacted for change to antibiotics if deemed appropriate, as is standard clinical practice. All study participants will have regularly 2-week and 6-week post-operative appointments where functional outcomes will be assessed in include physical exam, knee Lysholm scores and basic laboratory evaluation.

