Both [name] and [name] have served as statisticians in their previous roles as research assistants and have advanced training in statistical analysis. Regardless, the finalized data will be submitted to Texas Tech statisticians for validation and confirmation. Some of the anticipated statistical analysis tests are as follows:

Independent samples t-tests will be used to compare means of continuous and ordinal variables and p values less than 0.05 will be considered to represent a significant difference. For variables with Levene's Test for Equality of Variances greater than 0.05, equal variance is assumed. Pearson Chi-Square test p-values less than 0.05 will be considered to represent a significant difference in categorical variables. Fischer's exact test less will not be utilized as NCDB groups with  $n < 10$  are not to be included. ANOVA will be used to calculate significant differences in continuous and ordinal variables that have more than two categories. Paired samples t test and repeated measures ANOVA will be used to determine the progression of individual patients over time for continuous and ordinal variables respectively. Wilk's Lambda p-value less than 0.05 will be considered significant for repeated measures ANOVA and pairwise comparison will be used to determine the location of significance. Binary logistic regressions will be used to calculate odds ratios. Multivariate binary logistic regression may be attempted for all

significant variables. Receiver Operator Characteristic (ROC) may be calculated for significant continuous variables to determine the existence of a threshold that maximized sensitivity and specificity. All analysis will likely be performed by [name] on SPSS version 25 (IBM Corp. Released 2018. IBM SPSS Statistics for Macintosh, Version 25.0. Armonk, NY: IBM Corp).

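### The over-time tests are described as within-patient change with no arm or arm-by-visit term, so as described they do not inform the open-versus-arthroscopic comparison

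*Combined protocol and SAP*

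**What the plan says.** The over-time methods stand in the protocol's study design section, item I (Methods of data analysis): "Paired samples t test and repeated measures ANOVA will be used to determine the progression of individual patients over time". The same sentence then divides the two tests by type of variable: "for continuous and ordinal variables respectively". The last word of that sentence gives the paired t-test to continuous variables and repeated measures ANOVA to ordinal ones. The criterion that follows for the ANOVA is Wilks' Lambda below 0.05 and then pairwise comparisons. It does not say which effect is tested.

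Item I opens its list with a two-group method: "Independent samples t-tests will be used to compare means of continuous and ordinal variables". It does not say which groups, outcomes or visits this applies to.

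The aims are comparative. Specific Aims says: "Secondary outcomes will evaluate differences in knee range of motion, post operative pain levels, and overall patient satisfaction". The Abstract says: "Secondary outcomes included differences in functional outcome and overall patient satisfaction".

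The repeated data come from clinic visits at 2 and 6 weeks after surgery, where, according to item E (Schedule of events), "functional outcomes will be assessed in include physical exam, knee Lysholm scores" and basic laboratory tests.

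**The concern.** The trial asks whether the two approaches differ. A test of whether patients change between visits answers another question, because its result depends on the average change over everyone tested. It can be clearly significant when the arms are identical. The only methods that the plan gives for repeated data are described in this way, so the second visit adds nothing specified to the arm comparison. With about 20 patients per arm, that information is worth using.

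A separate and smaller matter is the split by variable type. Paired t-test or repeated measures ANOVA is a choice about the number of time points. Neither is an ordinal method.

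**Working it through.** **Plan's own figure.** None bears on this point. The stated minimum of 40 patients concerns the number of surgeries, and no effect size or SD is given for any outcome.

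**1. What the within-patient test estimates.** Let the mean change from 2 to 6 weeks be d1 in the open arm and d2 in the arthroscopic arm, with equal arm sizes. A paired test on all patients tests (d1 + d2)/2 = 0. A comparison of change between arms, which with two visits is the arm-by-visit interaction, tests d1 − d2 = 0. The first quantity does not determine the second.

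A simulation illustrates this. It used 20 patients per arm (about the plan's minimum), two visits, outcome SD 1, between-visit correlation 0.5 and 20,000 runs. All inputs except the arm size are assumed.

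| True change, arm 1 / arm 2 (SD) | Paired test on all patients significant | Between-arm test of change significant |
|---|---|---|
| 0 / 0 | 5.0% | 5.3% |
| 0.5 / 0.5 | 87% | 5.1% |
| 0.9 / 0 | 73% | 79% |

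The paired test is significant more often when the arms change equally (87%) than when only one arm changes (73%). It follows the average change, which is 0.5 and 0.45 SD in these two rows.

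**2. The continuous/ordinal split.** With two visits, the within-patient F statistic of a repeated measures ANOVA without an arm term equals the square of the paired t statistic: F(1, n − 1) = t², with the same p-value. With only the 2- and 6-week visits, the split therefore sends both variable types to the same test of means. Pairwise comparisons to locate an effect have a role only with three or more time points.

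**3. What using both visits gains.** Assume complete data, equal variance σ² at each visit and between-visit correlation ρ. With n per arm:

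- Variance of the arm difference at one visit: 2σ²/n
- Variance of the arm difference averaged over two visits: (2σ²/n) × (1 + ρ)/2
- Ratio: (1 + ρ)/2

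| ρ (assumed) | Variance ratio | Variance reduction | SE ratio | SE reduction |
|---|---|---|---|---|
| 0.4 | 0.70 | 30% | √0.70 = 0.837 | 16% |
| 0.6 | 0.80 | 20% | √0.80 = 0.894 | 11% |
| 0.8 | 0.90 | 10% | √0.90 = 0.949 | 5% |

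For the 6-week difference alone, a model with arm, visit, arm-by-visit and unstructured covariance reproduces the difference in 6-week means when data are complete. The gain there is zero.

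**The case against.** The strongest reply is that the plan already has a between-arm test. In a two-arm trial, independent samples t-tests are naturally read as comparing the arms, and the over-time tests are never offered as the answer to the secondary aim. This stands in part. A reader might infer that the secondary aim has no usable test at all, and the documents do not support that. What remains is that the t-tests take one visit at a time and are not linked to an arm, outcome or visit.

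Second, a repeated measures ANOVA can carry an arm factor, and the Wilks' Lambda sentence leaves the effect open. This also stands: the text is silent on an arm term and does not rule one out.

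Third, a reader might infer that paired tests will be run in each arm separately and then contrasted, with one arm significant and the other not taken as a treatment difference. Such a contrast would be unsafe, but the plan does not propose it, so no error rate from it should be charged to the plan.

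Fourth, the ordinal mapping does not cause the missing arm contrast. Treating ordinal values as interval would not remove an arm term, and the documents label no outcome as ordinal. The two points are independent.

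Fifth, the precision gain is modest and belongs to the visit-averaged difference, which is a different quantity from the 6-week difference. With complete data, a t-test on each patient's mean over the two visits would give the same averaged estimate.

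Finally, the list is presented as anticipated tests, to be validated by institutional statisticians. That makes a change easy, and is a reason to make it before results are seen.

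**Conclusion.** The point holds in a limited form. As described, the over-time analyses concern within-patient change only and specify no arm or arm-by-visit term, so they do not inform the comparison of approaches. The plan is not without a between-arm test, but the one it lists works visit by visit and is not assigned to any outcome.

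The benefit of a longitudinal model is an over-time analysis that answers the trial's question, plus a variance 10% to 30% lower for the visit-averaged difference. That range rests on an assumed correlation of 0.8 to 0.4, equal variances at the two visits and complete data. The wrong pairing of tests with variable types is a separate, minor error of wording. Overall this is a desirable improvement and does not threaten the trial's main conclusions.

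**What to change.** In item I, replace the paired t-test and repeated measures ANOVA sentence with the following:

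- For repeated continuous outcomes at 2 and 6 weeks (Lysholm score, and range of motion if it is recorded at the physical examination), fit a linear mixed model with assigned arm, visit and arm-by-visit, with unstructured covariance within patient.
- Report the arm difference at 6 weeks and averaged over the two visits, each with a 95% interval.
- Compare arms on any ordinal outcome by Mann-Whitney test or a proportional-odds model.
- Give within-arm change descriptively only, without a test.

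Pain and satisfaction are named as secondary outcomes in Specific Aims, but neither is named in the 2- and 6-week assessments or in the list of key variables. Their scale and timing should be stated before a model is assigned to them.

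The cost is a change of wording and slightly more analysis work. For the outcomes already collected at these visits, it needs no new patients, visits or measurements.

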All non-english speaking persons will be offered study inclusion. Informed consent will be obtained utilizing a Spanish-translated consent form (after IRB approval). There are multiple Spanish speaking members of the research personnel and they will be obtaining Spanish consents. If one is not available, then a certified hospital interpreter will be utilized. If none are available, since UMC does not allow language line solutions to be used for research purposes, the patient will not be able to be consented and thus will not be included in the study.

C.) Indicate the population of subjects potentially able to participate in this study

All adult patients (>18 years) who have a clinically established diagnosis of septic arthritis in the emergency department based on the following will be considered for study inclusion and approached for offering participation in our study:

- Arthrocentesis with synovial WBC > 50,000 with left shift (85% PMNs)
- AcrySTALLINE (without gout crystals) elevated synovial WBC >25,000 with high clinical suspicion
- Willingness to participate in this research study

These patients are all indicated with formal operative irrigation and debridement of their knee, regardless of study inclusion. However, they will be excluded from study inclusion if they meet one of the following exclusion criteria:

- Recently treated septic arthritis (within past 3 months)
- If they have a prosthetic joint replacement to the affected knee
- Refusal to participate in the study

D.) Indicate the number needed

Our power analysis (beta =0.80, alpha = 0.05) shows the optimal sample size to be a minimum of 40 patients.

E.) List the inclusion/exclusion criteria

All adult patients (>18 years) who have a clinically established diagnosis of septic arthritis in the emergency department based on the following will be considered for study inclusion and approached for offering participation in our study:

- Arthrocentesis with synovial WBC > 50,000 with left shift (85% PMNs)
- AcrySTALLINE (without gout crystals) elevated synovial WBC >25,000 with

high clinical suspicion  
-Willingness to participate in this research study

These patients are all indicated with formal operative irrigation and debridement of their knee, regardless of study inclusion. However, they will be excluded from study inclusion if they meet one of the following exclusion criteria:

- Recently treated septic arthritis (within past 3 months)

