- If they have a prosthetic joint replacement to the affected knee
- Refusal to participate in the study

F.) Vulnerable populations

Patients with altered mental status at the time of presentation. In accordance with current guidelines, a legally authorized representative may provide consent for inclusion in this study. If a legally authorized representative is unavailable, the patient will not be considered for inclusion in this study.

G.) Describe the method of identifying and recruiting subjects and any screening

All adult patients (>18 years) who have a clinically established diagnosis of septic arthritis in the emergency department based on the following will be considered for study inclusion and approached for offering participation in our study:

- Arthrocentesis with synovial WBC > 50,000 with left shift (85% PMNs)
- AcrySTALLINE (without gout crystals) elevated synovial WBC >25,000 with high clinical suspicion
- Willingness to participate in this research study

These patients are all indicated with formal operative irrigation and debridement of their knee, regardless of study inclusion. However, they will be excluded from study inclusion if they meet one of the following exclusion criteria:

- Recently treated septic arthritis (within past 3 months)
- If they have a prosthetic joint replacement to the affected knee
- Refusal to participate in the study

H.) Define how long each subject will be studied

Approximately 6 weeks after discharge (the hospital length of stay will be variable depending on patient comorbidities).

I.) Describe any compensation given to subjects

This study will NOT be offering compensation to any subjects.

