**Describe the following aspects of the study design:**

A.) Proposed study groups with number/group and treatments/group

Group 1: patients who undergo open surgical incision and drainage with debridement and irrigation (>20 patients)

Group 2: patients who undergo arthroscopic incision and drainage with debridement and irrigation (>20 patients)

B.) Describe the method used to determine the number of subjects needed

Power analysis utilized to determine a difference in the number of surgeries required to display apparent clinical resolution between open versus arthroscopic treatments (beta =0.80, alpha = 0.05) shows the optimal sample size to be a minimum of 40 patients.

C.) Describe how you determined that this number of subjects could be recruited

Power analysis. Additionally, [name] (CHRC/Research Manager MC EP Compliance) was contacted and was able to find a preliminary potential of 1,851 unique patient records from the year 2000 to the present who had septic arthritis. Even if only 20% of these patients met study inclusion/exclusion criteria, approximately 20 patients a year would be included. This would require 2-3 years of data collection in order to meet appropriate power analysis.

Anecdotally, the attending physicians serving as principal- and co-investigators believe they treat a minimum of 20 adult patients each per year with septic arthritis of the native knee.

D.) Method of randomization

Patients with medical record numbers ending in an EVEN number will undergo open surgical irrigation and debridement.

Patients with medical record numbers ending in an ODD number will undergo arthroscopic surgical irrigation and debridement.

E.) Schedule of events (i.e. control vs. treatment, number of visits)

All patients who present to the emergency department with a painful knee and clinical suspicion for septic arthritis undergo appropriate workup by the emergency department staff members. If there is a clinical suspicion for septic arthritis, the standard workup includes the following:

- assessment of vitals
- obtaining a history of the present illness
- performing an appropriate physical examination

If a provider determines that septic arthritis is part of their differential diagnosis, a basic serum laboratory workup is to be ordered. There will be a template created on the Cerner application to assist providers with a convenient, expedited manner of ordering these labs. These will include the following blood serum values:

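### The Wilks' lambda ANOVA and paired t-tests drop partly observed patients from each over-time analysis; a mixed model would keep them, for a modest gain

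*Combined protocol and SAP*

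**What the plan says.** The methods of data analysis (item I of the study design section) state: "Paired samples t test and repeated measures ANOVA will be used to determine the progression of individual patients over time". The same sentence gives the paired t-test to continuous variables and the ANOVA to ordinal ones. The next sentence sets the decision rule: "Wilk's Lambda p-value less than 0.05 will be considered significant for repeated measures ANOVA". The work is expected to be done "on SPSS version 25", but no procedure or missing-data option is named.

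The schedule of events (item E) says "All study participants will have regularly 2-week and 6-week post-operative appointments", at which the assessments are "physical exam, knee Lysholm scores and basic laboratory evaluation". Laboratory values and examination findings are also taken at presentation. No presentation Lysholm score is scheduled. Each patient is studied for "Approximately 6 weeks after discharge", so no later visit can stand in for a missed one.

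Neither the analysis section nor the sample size text gives a rule for missed visits, an attrition allowance, imputation or a mixed model.

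**The concern.** Wilks' lambda is computed from each patient's full set of repeated values, so a patient who lacks one occasion contributes nothing to that model, even though the visit attended was recorded. The paired t-test has the same requirement for the two visits it compares. For Lysholm, with two scheduled occasions, the two methods are equivalent and the patient is lost either way. Adding an arm term to the same ANOVA would not restore these patients.

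Two things are at stake. With about 40 patients, precision on functional and laboratory recovery is lost although the data exist. The result also describes only patients who attended everything required, which can mislead if attendance depends on how the knee is doing.

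**Working it through.** **The plan's own figure.** The protocol says: "Our power analysis (beta =0.80, alpha = 0.05) shows the optimal sample size to be a minimum of 40 patients". It gives no effect size or standard deviation, so 40 cannot be reproduced. Reading 0.80 as power, 20 per arm and a two-sided test imply a standardised difference of (1.960 + 0.842) × √(2/20) = 0.886. That calculation concerns number of surgeries, and only N = 40 is used below.

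**Inputs**
- From the documents: N = 40; follow-up at 2 and 6 weeks; Lysholm at those two visits only; laboratory values and examination also at presentation.
- Assumed, because the documents are silent: a fraction m missed independently at each follow-up visit (10, 15 or 25%); presentation values complete; equal variances; a common within-patient correlation ρ of 0.4–0.7 for two occasions and 0.4–0.6 for three; missingness unrelated to outcome for the precision figures.

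**Step 1: patients retained**

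| m | Both visits, 40(1−m)² | At least one, 40(1−m²) | Same patients miss both, 40(1−m) |
|---|---|---|---|
| 10% | 32.4 | 39.6 | 36 |
| 15% | 28.9 | 39.1 | 34 |
| 25% | 22.5 | 37.5 | 30 |

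The last column is the milder case. Those patients have no follow-up visit, so for Lysholm a mixed model recovers nothing from them.

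**Step 2: 2-to-6-week change with two occasions (Lysholm)**
- Complete pairs: variance = 2σ²(1−ρ) / [N(1−m)²].
- Mixed model, covariance known: variance = 2σ² / {N[(1−m)²/(1−ρ) + m(1−m)]}.
- Ratio of standard errors = √[1 + m(1−ρ)/(1−m)].

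| m | ρ = 0.4 | ρ = 0.7 |
|---|---|---|
| 10% | √(1 + 0.10×0.6/0.90) = 1.033 | √(1 + 0.10×0.3/0.90) = 1.017 |
| 15% | √(1 + 0.15×0.6/0.85) = 1.052 | √(1 + 0.15×0.3/0.85) = 1.026 |
| 25% | √(1 + 0.25×0.6/0.75) = 1.095 | √(1 + 0.25×0.3/0.75) = 1.049 |

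The planned analysis has a standard error 2–10% larger.

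**Step 3: presentation-to-6-week change with three occasions**
- ANOVA, all three values required: variance = 2σ²(1−ρ) / [N(1−m)²].
- Paired t-test, 2-week value not needed: variance = 2σ²(1−ρ) / [N(1−m)].
- Mixed model: for each pattern of attended visits, take the inverse covariance matrix of the observed values, weight by the pattern's probability, sum and multiply by N. Invert the total and apply the contrast (−1, 0, 1).

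| m | ANOVA SE / mixed model SE | Paired t-test SE / mixed model SE |
|---|---|---|
| 10% | 1.07 | 1.02 |
| 15% | 1.11 | 1.02–1.03 |
| 25% | 1.20–1.21 | 1.04–1.05 |

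The two columns differ by the factor 1/√(1−m): 1.054, 1.085 and 1.155. Simulated 40-patient data sets agree to within about one percentage point. A known covariance slightly favours the mixed model; estimating it at this size would trim these gains.

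**Step 4: bias.** If missed visits are unrelated to outcome, complete-case estimates lose precision only. If they depend on a value that was recorded, such as the 2-week score, the complete-case change is in general biased, while a correctly specified mixed model is not. If they depend on the unseen value, neither is protected. The documents give no basis for a size.

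**The case against.** The strongest counter-argument is about scope, and most of it stands. A reader might infer that one missed visit removes all of a patient's data from the over-time analyses. The documents do not support that. The plan gives continuous variables to paired t-tests and ordinal ones to the ANOVA, so a presentation-to-6-week laboratory pair survives a missed 2-week visit. Against that planned test the mixed model gains only 2–5%. The larger 7–21% range applies only where the ANOVA is run over three occasions.

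A reader might also infer that the Wilks' lambda rule makes the 6-week Lysholm comparison between arms less precise or biased. It does not. The plan compares group means with independent samples t-tests, which keep everyone seen at that visit. Such a test can be biased by outcome-related missed visits, but the cause would be absent 6-week scores, not deletion by Wilks' lambda.

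Further points are fair. The tests are described as anticipated, with institutional statisticians to validate the results. No missed-visit rate is given. The two main outcomes, length of stay and number of surgeries, are not analysed this way. Still, the plan names no alternative for incomplete follow-up, and the loss of single-visit patients from the Lysholm change remains.

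**Conclusion.** The point holds in a narrow form and is minor. The ANOVA judged by Wilks' lambda excludes anyone lacking an occasion of that measure. The paired t-test excludes anyone lacking either visit of its pair. For Lysholm, one missed visit of two is enough.

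The loss could reach 8 to 18 of 40 patients in an affected model, but the precision cost is modest except for ANOVA over three occasions. These sizes rest on assumed missed-visit rates and correlations and on independent misses; they shrink if the same patients miss both visits. The possible bias is real in kind but cannot be sized from the documents. The case for changing is that recorded data would be kept at almost no cost.

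**What to change.** Replace the Wilks' lambda rule and the paired t-tests with one linear mixed model per continuous or score measure: SPSS MIXED, REML, unstructured covariance and Satterthwaite degrees of freedom. Include visit as a factor, arm, and arm-by-visit. Use every patient with at least one recorded visit. Take both the visit contrasts and the arm difference at each visit from this model. The arm terms matter: a model with visit alone could not estimate the arm difference and would leave it to the separate t-tests. State the missing-data assumption alongside, with a sensitivity analysis.

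The cost is a change of wording and slightly more analysis work in software already named; no new data are needed. The downsides are that the model assumes missingness is explained by the recorded data, and that its degrees of freedom are approximate at about 40 patients.
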